11 QUALITATIVE EVALUATIONS

11.1 CYP and Parent Interviews

Interviews will be conducted in person or over video call at the end of FES intervention (week 20) (see figure 1). In person interviews will be in the CYP home with their permission. The interviews will be conducted by the SC following topic guides developed from the TFA. Each interview will last approximately 45 minutes and will follow the interview schedule outlined in Appendix 5.

[figure not shown]
12.RECRUITMENT

Recruitment will take place simultaneously across each Child Development Centres (CDCs) and Community Paediatric Outpatient physiotherapy services. These include Plymouth Hospitals NHS Trust, Torbay and South Devon NHS Trust, Royal Cornwall Hospitals NHS Trust and Royal Devon and Exeter NHS Trust. The study will be advertised via interest groups, University of Plymouth website and charity / support group websites (e.g Cerebra). In preparation for recruitment, the SC will visit each site to familiarise physiotherapists with the eligibility criteria and study procedures.

Potential study participants will be identified, screened, and recruited as shown in Figure 9.

Figure 9. Diagram of recruitment

- Recruitment will take place simultaneously in each NHS trust, the university of Plymouth and via social media
- In preparation for recruitment the SC will visit each recruiting sites to familiarise recruiting clinicians with eligibility and study procedure.
- Once a child has been recruited and identified as a suitable candidate to
 participate in the study the SC will contact their parents to arrange an
 appointment for them attend the study assessment at the University of
 Plymouth.

Health Research Authority

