3.	To explore how Functional Electrical Stimulation applied to either the Quadriceps during stance phase of gait or Tibialis Anterior during swing phase of gait over an 8-week period affects parents' perception of gait and child's perception of fatigue and gait in children with cerebral palsy and crouch gait	Parent and Child completion of the Gait Outcomes assessment List (GOAL) questionnaire Child completion of the Neuro-QOL paediatric fatigue short form and 12-ltem Walking Scale Post FES Semi structured interview with parents and children/young people exploring perception of FES intervention on gait function and mobility.

Health Research Authority

3.	To explore the acceptability of FES intervention and study participation	Semi-structured interviews informed by the constructs described in the Theoretical Framework of Acceptability
4.	To monitor adherence to a an 8-week FES intervention with FES being applied to either the Quadriceps during stance phase of gait or Tibialis Anterior during swing phase of gait in children with cerebral palsy and crouch gait.	 FES activity logger recordings of duration of use (HH:MM) and number of steps taken.
		Post FES Semi structured interview with parents and children/young people exploring barriers to adherence to FES intervention.

FUNDING AND SUPPORT IN KIND

FUNDER(S)	FINANCIAL AND NON-FINANCIAL SUPPORT GIVEN
Torbay Medical research Fund	Financial Support of the study via a clinical
[contact]	doctoral fellowship which includes the cost of the
	backfill for my clinical hours.
University of Plymouth	Academic Support

ROLE OF TRIAL SPONSOR AND FUNDER

The Sponsor organisation is University of Plymouth. The Sponsor Representative is [name] - . The sponsor's responsibilities are as defined in the UK policy framework for health and social care research (version 3.3 2017).

Tasks associated with meeting various sponsorship responsibilities have been delegated to the CI or by way of formal agreement.

Torbay Medical Research Fund, funds this study as part of a Clinical Doctoral Fellowship. The role of the funder is to fund the trial. The Sponsor nor funder have no direct role in trial design, data analysis and interpretation, manuscript writing or dissemination of results.

ROLES AND RESPONSIBILITIES

Study Steering Committee and study management group

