- 3.2 To explore the impact of FES applied to either the Quadriceps during stance phase of gait or Tibialis Anterior during swing phase of gait over an 8-week period to the most affected limb on impairment profile (quadriceps and tibialis anterior strength, passive range of hip flexion; knee flexion and ankle dorsiflexion, selective motor control), in children with crouch gait and cerebral palsy.
- 3.3 To explore how FES applied to either the Quadriceps during stance phase of gait or Tibialis Anterior during swing phase of gait, over an 8-week period, affects parents' perception of gait and child's perception of fatigue and gait in children with cerebral palsy and crouch gait
- 3.4 To explore acceptability, study participation and adherence to an 8-week FES intervention with FES being applied to either the Quadriceps during stance phase of gait or Tibialis Anterior during swing phase of gait in children with cerebral palsy and crouch gait.

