4. STUDY DESIGN

Using SCS we aim to examine the effect of FES applied to the quadriceps muscles for 2-4 hours a day, 6 days a week, over an 8-week period in children with CP who have a crouch gait. The FES application and stimulation parameters will follow previous work [16].

The effects of FES will be investigated using an AB single case study design. There will be an initial 8-week baseline period over which serial outcome measures (walking, muscle strength and perceived walking ability and fatigue) will be taken (figure 1). The FES will be issued in week 9 with a one-week period to determine the optimal simulation parameters. There will then be 8 weekly assessments while the FES being used (week 10-18). There will be a final assessment at week 20 where a semi-structured interview will occur (figure 1). At the start and end of each phase (weeks 1, 8, 10, 19) there will be a more in-depth assessment of impairment (muscle strength, passive range of motion and selective motor control).

The research question can be framed as follows:

Population: Ambulatory Children with bilateral Cerebral Palsy, age 8-18 years old, GMFCS level I-III

Intervention: Functional Electrical Stimulation applied to the quadriceps during stance phase of gait or Tibialis anterior during the swing phase of gait for 2-4 hours a day, 6 days a week

Time: 8 weeks FES intervention

Outcome:

[figure not shown]
Primary: The effect of FES on knee flexion angle during mobility tasks (walking on the flat and up/downstairs), as measured by an electric goniometer at initial contact and midstance.

Secondary: Effect of FES on:

- Muscle strength, passive range of motion, selective motor control.
- Parents' perception of gait and child's perception of fatigue and gait
- Acceptability of FES as an intervention for crouch gait using semi structured interviews with parents and children/young people.

Health Research Authority

Figure 1. Study timeline diagram

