6. PARTICIPANTS ELIGIBILITY CRITERIA

6.1 Inclusion Criteria

 Diagnosis of spastic CP (GMFCS level I-III), affecting one or more muscle groups in both lower limbs, and aged 8-18years

- 2. The ability to follow simple instructions.
- 3. The ability to adhere to the FES protocol.
- 4. The ability to walk 20 metres of more with or without a walking frame.

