During FES Set Up, the participant will experience the sensation of FES activating the muscle for the first time, for some CYP this can be uncomfortable to begin with. They will be given time to get used to the sensation and can stop for comfort breaks if required. If the CYP is unable to tolerate the sensation, they can ask to stop the session and may wish to withdraw from taking part in the study. Once the FES device is set to a level that a contraction is observed in either Tibialis Anterior or the Quadricep, the SC will stick the foot switch into a cork insole, which can then be placed in the child's shoe. In most cases the foot switch will be placed in the heel of the insole (see figure 8A), but if the child is not achieving a heel strike at initial contact, the foot switch will need to be placed under the head of the first metatarsal (see figure 8B). Once the foot switch is connected to the FES device the participant is ready to trial using the FES when walking. For FES tibialis anterior set up, the FES device will be set to activate tibialis anterior when the heel or forefoot rises off the floor and through swing phase of gait. For FES quadricep set up the device will be set to activate the quadricep at initial contact and early stance phase of gait. Once the child is walking with the FES the SC may have to make further adjustments to the timing and speed of the muscle activation for optimal gait performance

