15.2 Qualitative data

To determine the feasibility, acceptability and safety of the intervention interviews will be analysed using the five iteratives stage of the Framework Analysis method (familiarisation, thematic framework identification, indexing, charting, mapping and interpretation) [30]. This method incorporates both deductive and inductive coding and provides a strong audit trail of the analytical process from original transcripts to final themes, including illustrative quotes [31], and enables trial processes and positive as well as negative participant experiences to be explored and reported. Deductive trial factors will include factors relating to feasibility, acceptability and adoption of technology which will be informed by the theoretical framework of acceptability [32] and the NASSS Framework [33].

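### The only acceptability interview is planned for week 20, with none at withdrawal, so children who withdraw because they cannot tolerate FES drop out of the acceptability findings

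*Protocol*

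**What the plan says.** Objective 3.4 reads in part: "To explore acceptability, study participation and adherence to an 8-week FES intervention". In the Trial Summary and in the table in section 13.2, the measure for the acceptability objective is given as "Semi-structured interviews informed by the constructs" of the Theoretical Framework of Acceptability, and no other instrument is listed. Adherence has two sources, the FES activity logger and the interview.

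The interview is timed in two places, and they agree. Section 4: "There will be a final assessment at week 20 where a semi-structured interview will occur (figure 1"). Section 11.1: "Interviews will be conducted in person or over video call at the end of FES intervention (week 20").

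Section 15.2 gives the interviews a broad role: "To determine the feasibility, acceptability and safety of the intervention interviews will be analysed" by the Framework method, with negative as well as positive experiences in scope.

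On leaving the study, section 10.1 says that if a child at the week-9 set-up is "unable to tolerate the sensation, they can ask to stop the session and may wish to withdraw from taking part in the study". Section 12.6 allows withdrawal at any time without a reason. It says that data collected up to then will be used unless the family wants them destroyed. Neither section mentions an interview at withdrawal.

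**The concern.** The children for whom FES proved intolerable carry much of the information on acceptability. If such a child withdraws at week 9, the one planned interview lies 11 weeks ahead, at a visit the family will no longer attend. Whether acceptability data exist then depends on acceptability itself, and no later analysis can recover what was not collected.

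Section 2 says the series is meant to inform a future randomised trial. Themes drawn mainly from families who stayed would tell the designers of that trial too little about early intolerance and the barriers behind it. Who is approached for interview, when, and what families are told about it in advance are matters of conduct. They belong in the protocol and the information sheet and cannot be left to an analysis plan.

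**Working it through.** There is no figure in the plan to reproduce: section 15.3 sets the sample of 12 from resources and time, not from a formula. The check is therefore mainly one of setting the sections side by side.

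**Path of a child who withdraws for intolerance at set-up**

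1. Week 9: FES is felt for the first time (section 10.1), and withdrawal is foreseen as a possibility.
2. Data kept: those gathered up to withdrawal (section 12.6). These are baseline-phase measures, taken before any FES.
3. Logger: data are collected weekly during the FES intervention (section 9.2.3), which begins in week 10 (section 10.4). This child has none.
4. Reason for leaving: need not be given (section 12.6).
5. Interview: week 20 only (sections 4 and 11.1), and none at withdrawal.

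The child contributes nothing to the acceptability part of objective 3.4 unless approached outside the written plan.

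**Path of a child who stops or reduces FES but stays in the study**

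This child reaches week 20 and can be interviewed. The schedule in Appendix 4 asks about dislikes, problems or adverse effects, and what put the child off FES. Item 10 of the TIDieR table in Appendix 8 also allows FES to be modified for poor tolerance, so intolerance need not lead to withdrawal.

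**Fit of the interview schedule**

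Appendix 4 asks about change over the last 8 weeks and about the effect of using FES for 8 weeks. These questions do not fit a child who left at set-up.

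**Size, under assumptions**

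The protocol gives no rate of withdrawal or intolerance, so both lines below are illustrations.

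- Share of families without a planned interview if k of 12 withdraw: k/12. For k = 1, 1/12 = 8%. For k = 3, 3/12 = 25%.
- Chance that at least one of 12 children withdraws for intolerance, at an assumed probability p per child, taking children as independent: 1 − (1 − p)^12.

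| Assumed p | Expected number, 12p | Chance of at least one |
|---|---|---|
| 5% | 0.6 | 1 − 0.95^12 = 46% |
| 10% | 1.2 | 1 − 0.90^12 = 72% |
| 20% | 2.4 | 1 − 0.80^12 = 93% |
| 30% | 3.6 | 1 − 0.70^12 = 99% |

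At modest assumed rates, at least one such withdrawal is about as likely as not or more so. In a series of 12, one or two missing accounts matter.

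**The case against.** The strongest reply is that section 11.1 sets a time and not an eligibility rule. Nothing limits interviews to children who finished the course, and nothing bars contact with families who have withdrawn. A reader might infer that children who stop FES are never asked, or that only completers are interviewed. The documents do not support that: stopping FES is not the same as leaving the study, and those who stay reach week 20. This part of the objection stands in full.

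Nor does the protocol say that it expects children to withdraw at week 9. Section 10.1 expects initial discomfort for some children, and treats intolerance and withdrawal as conditional. Section 12.6 says data up to withdrawal will be used, and does not forbid an exit conversation. These corrections also stand. The point here is that no interview is provided for, which is different from one being ruled out.

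Section 19.1 names an exit questionnaire among the documents for ethics approval. It may be a remedy, but its content, timing and recipients are not described and it is not listed as an outcome measure. It cannot be counted as closing the gap, and it cannot be ignored either.

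Finally, a child who stops partway through the course leaves logger data (section 9.2.3) and weekly adverse event reports (section 17.1). That is true and useful for adherence and safety. It does not supply the family's view of acceptability, and it does not help for a child who leaves at set-up before any weekly logger data exist.

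**Conclusion.** The point holds in a limited form. Interviews are the only listed measure of acceptability, they have one planned time, and none is provided at withdrawal. Children who withdraw because they cannot tolerate FES would therefore be absent from this part of objective 3.4 unless approached outside the plan, and the themes would lean towards families who stayed. That sits badly with the aim in section 15.2 of exploring negative experience.

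The size is unknown. Under the assumption that 1 to 3 of 12 withdraw, 8% to 25% of families have no planned interview. Not all of these need be withdrawals for intolerance.

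Two stronger readings should be resisted. First, a reader might turn these counts into a true acceptance rate. The objective is qualitative, no such proportion is planned, and completing the course is not the same as accepting it. Second, a reader might see inclusion criterion 3, "The ability to adhere to the FES protocol", as having already filtered the sample towards acceptance. The criterion concerns ability to adhere, and stimulation is first felt at week 9, so screening cannot select on how well a child tolerates it.

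**What to change.** - **Section 11.1:** offer a voluntary interview to every child and parent who reached the week-9 set-up, at week 20 or soon after withdrawal, whichever comes first. For those who withdraw, use a shortened version with the 8-week wording in the Appendix 4 schedule adapted. Say in the information sheet that this interview will be offered.
- **Section 15.2:** beside the themes, report how many children stopped FES and how many withdrew, with any reasons they volunteered, against all who started set-up.
- **Section 19.1:** state what the exit questionnaire covers, who receives it and when, and whether it is meant to serve this purpose.

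The cost is small: brief text in the protocol and information sheet and light rewording of the schedule. The same interviewer can be used, and no family has more than the one interview already planned. Some withdrawn families will decline, and section 12.6 rightly leaves them free to give no reason. The report should state how many declined.

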12.1 Estimation of recruitment rate

There are an estimated 1460 children with CP within the targeted age range and severity distribution in the South West of England, based on published prevalence data and population estimates from the Office for National Statistics (2015). Of these 71% of children are predicted to be ambulant, i.e. GMFCS levels I-III. We anticipate that within each NHS trust locality there will be approximately 150 children with a diagnosis of CP (Cerebral Palsy Integrated Pathway South West, 2017 unpublished data). Therefore, we predict that approximately 60-80 ambulant children with CP may be eligible in each NHS trust locality.

We aim to recruit 12 participants with CP across the three sites in Devon and Cornwall over a 6-month period. An estimated recruitment rate of two to four children per month over a maximal 10-month period has been calculated based on the population and previous experience.

12.2 Participant identification

Recruitment will primarily occur through clinical teams at 4 NHS Trusts: These include Plymouth Hospitals NHS Trust, Torbay and South Devon NHS Trust, Royal Cornwall Hospitals NHS Trust and Royal Devon and Exeter NHS Trust.

Participants will also be recruited via posters and adverts. These will be distributed in local newsletters of groups such as APCP (Association of Paediatric Chartered Physiotherapists) and PenCru (Peninsula Childhood Disability Research Unit). As well as online via social media sites such as facebook, Instagram and twitter on pages that are relevant to our study population, such as Cerebral Palsy UK, Cerebra, CP sport and SCOPE .

 Physiotherapists, occupational therapists, paediatricians and orthopaedic surgeons will identify potential participants during clinics and via their caseload lists. Clinicians may approach children on their caseloads by telephone before sending out an information pack to those who are interested in taking part. The information pack contains a contact reply slip, prepaid envelope and information sheet.

- Posters and leaflets will be produced for clinicians to distribute to potential
 participants. They will also be issued for clinicians to put up in departments
 and waiting rooms where children with CP may have appointments.
- Potential participants can contact the research team via contact details on posters / adverts or via a contact reply slip and prepaid envelope which is part of the information pack.
- When potential participants contact the research team they will be contacted
 via their preferred route (eg telephone / e mail) and the participant information
 sheet (PIS) will be sent out and later discussed to ensure that the parents /
 guardian and children understand the study prior to volunteering. The PIS will
 be available for parents and young adults (16-18 years) and an easy read
 version will be available for children.
- Consent forms will be provided to parents and, young adults, and assent forms provided to children when attending the appointment.
- Participants / guardians and or parents will be issued with PIS at least 24
 hours prior to their study appointment so that they have time to discuss the
 trial with the research team before participating.

12.3 Screening

The local PI will use a study-specific screening log to record numbers of children eligible, ineligible, the numbers of children approached, and numbers of study information packs given out at each site. Potential participants who respond to the invitation and will be screened for suitability using a telephone questionnaire to check diagnosis, age, GMFCS level, neuromusculoskeletal involvement and distribution and the child's ability to follow simple instructions.

12.4 Payment

Travel expenses (up to £30/visit) will be reimbursed for all assessment sessions taking place outside of the home. Travel expenses above this amount will be discussed on a case-by-case basis.

12.5 Consent

- Potential participants/parents and/or guardians will be issued with a PIS.
- Discussions will take place between the potential participant, their parent
 and/or legal guardian and a member of the research team. This will cover the
 nature of the study, the study procedure, the possible risks associated with
 participation, as well as their right to withdraw from the study at any time.
 Potential participants/parents and/or guardians will also be given the
 opportunity to ask questions.
- According to the Medicines For Human Use (Clinical trials) regulations, children under the age of 16 are prohibited from taking part in a clinical trial without the consent of a parent or legal guardian or representative. Therefore, in children under the age of 16 years old, the child's parents or their legal guardian will be responsible for signing and completing the written consent form. Assent from the child will be obtained through discussion with their parent or legal guardian and the CI.
- Young person's participating between 16 and 18 years of age who are considered capable of giving consent according to the Health Research Authority will have the opportunity to complete their own written consent form.
- Written informed consent and assent will be recorded at the start of the child's study appointment by the CI, before any study investigations can begin.

12.6 Withdrawal

Participants can withdraw at any point in the study without giving a reason. It will be emphasised that this would not affect their healthcare or potential involvement in another research. At the point of withdrawal from the study CYP data up to that point will be used for data analysis unless the CYP and/or parent express that they would like this data to be destroyed.

13 ASSESSMENT AND TESTING

13.1 Baseline data

GMFCS level

- Distribution of lower limb weakness
- Date of Birth
- Medical and surgical history
- Height, Weight,
- Presence and site of any pain
- Foot posture

